### 7.5 Overall Survival (OS)

- The interval between the date of first dose until the date of death or the date of last follow-up will be calculated.
- The OS rate, including the 95% CI, will be presented. Duration of follow-up will also be presented. OS will also be updated at yearly intervals during the Post Study Follow-up and can be provided as addendums to the final report.
- Subjects who are still alive will be censored on the date of last follow-up. Every effort will be made to follow subjects for OS after they discontinue the study.
- OS will be summarized using the 25th percentile, Median, and 75th percentile as well as the minimum and maximum survival time, calculated by Kaplan-Meier method, and will be displayed graphically

### 7.6 Duration of Response (DoR)

- Duration of response (DOR) will be calculated interval between the date of earliest determination of CR or PR to the date of first PD, clinical progression or death whatever occurs first. Patients who had a response and did not lose it subsequently and were alive will be censored at the time of last available tumor assessment.
- $DOR \text{ in weeks} = (\text{Earlier of Date of PD or death} - \text{date of first response} + 1) / 7$
- The median DOR with 2-sided 95% confidence intervals will be presented for subjects who have a confirmed CR or PR at 8 and 24 weeks.

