#### **4.2.1.3 Duration of Response (DoR)**

DoR is defined as the interval between the date of earliest determination of CR or PR to the date of earliest determination of PD, or to the date of death, if PD does not occur.

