### 3.0 GENERAL ANALYSIS CONVENTIONS

#### 3.1 General Conventions

Data collected in this study will be documented using summary tables and subject data listings. Continuous endpoints will be summarized using descriptive statistics, e.g. number of subjects, mean, median, standard deviation, minimum and maximum values. The mean and median will be reported to 1 decimal place more than the level of precision of the data being reported and the SD will be reported to 2 decimal places more than the level of precision of the data being reported, unless otherwise noted. Categorical endpoints will be presented in frequency tables with number and percentage of observations for each level.

All efficacy analyses will be presented separately for Arm A and Arm B. Tumor Response will be summarized and analyzed descriptively. A 95% Confidence Interval based on the binomial distribution will be constructed for the estimated PFS rate and ORR at 8 and 24 weeks and DCR.

The number and percentage of subjects who died or had a confirmed progression, who survived without a confirmed progression, and who were lost to follow up (unknown survival and/or progression status) will be summarized.

PFS rate at 8 and 24 weeks and the corresponding 95% CIs will be calculated based on Kaplan-Meier product limit estimates and will be displayed along with the corresponding number of subjects at risk. (Note – this may include OS as well)

PFS and OS will be summarized using the 25th percentile, Median, and 75th percentile as well as the minimum and maximum survival time, calculated by Kaplan-Meier method, and will be displayed graphically.

The ORR, DCR and DOR will be summarized descriptively and a 95% Confidence Interval based on binomial distribution will be presented.

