### 7.2 Objective Response Rate (ORR)

- Objective Response Rate (ORR) is defined as the percentage of subjects meeting criteria of Complete Response (CR) or Partial Response (PR).
- To be assigned a status of a CR or PR, changes in tumor measurements must be confirmed by repeat assessments that must be performed at least 4 weeks after the criteria for response are first met. If a response is not confirmed, it is considered stable disease.
- If a subject had clinical progression (CP), any recorded response (CR or PR) after the date of CP will be considered invalid.

- Subjects who drop out prior to having a response assessment (including clinical progression) for ORR will be considered as non-responders and they will be included in the denominator when calculating the proportion.
- A 95% Confidence Interval based on binomial distribution will be constructed for the estimated ORR at 8 and 24 weeks.

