### 7.7 Analysis of Time to Event (TTE) Variables

Progression Free Survival (PFS), OS and DoR will be analyzed using the Kaplan-Meier product limit estimates along with the corresponding number of subjects at risk. The Duration of follow-up (in months) will be analyzed using the Reverse Kaplan-Meier product limit estimation method.

For all time to event analyses the number of events, number censored, 25th percentile, median, 75th percentile, corresponding 95% CIs as well as the minimum and maximum survival time will be presented in tables. In addition, survival curves will be presented graphically.

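### SAP 3.1 gives duration of response a binomial confidence interval, and SAP 7.6 ties its median to an undefined 8- and 24-week responder set; Kaplan-Meier DoR in all confirmed responders should replace both

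*SAP*

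**What the plan says.** **Definition.** Protocol 4.2.1.3: "DoR is defined as the interval between the date of earliest determination of CR or PR to the date of earliest determination of PD", with death as the end point when there is no progression. SAP 2.2 repeats this. The first bullet of SAP 7.6 adds clinical progression as an end point and makes DoR a censored time: "Patients who had a response and did not lose it subsequently and were alive will be censored" at the last available tumor assessment. None of these passages names a landmark visit.

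**Who is reported.** The last bullet of SAP 7.6 says the median, with a two-sided 95% interval, "will be presented for subjects who have a confirmed CR or PR at 8 and 24 weeks".

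**How it is estimated.** SAP 7.7 says PFS, "OS and DoR will be analyzed using the Kaplan-Meier product limit estimates". It continues "For all time to event analyses the number of events, number censored", followed by quartiles, their 95% intervals, minimum and maximum. It names no subset of responders.

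**Which interval.** SAP 3.1: "The ORR, DCR and DOR will be summarized descriptively and a 95% Confidence Interval based on binomial distribution will be presented". Protocol 4.2.2 gives a binomial interval to PFS rate and ORR at 8 and 24 weeks and to DCR. DoR is not on that list.

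**Confirmation.** Under SAP 7.2 a response "must be confirmed by repeat assessments that must be performed at least 4 weeks after the criteria for response are first met". It adds: "If a response is not confirmed, it is considered stable disease".

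**The concern.** Two rules in the SAP, followed as written, do not produce the DoR that the protocol defines. SAP 3.1 asks for an interval that cannot be formed for a censored duration. SAP 7.6 asks for a median in a responder set that is narrower than the one implied elsewhere and is not clearly defined. With few responders expected in an arm of 20, moving one subject in or out of the set can move the median. The choice between readings would then be made after the responses are known.

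**Working it through.** **1. The binomial interval.** The planning table in Protocol 3.1.6 shows what such an interval is. For x events in n subjects, the Clopper-Pearson limits are the 2.5% quantile of Beta(x, n − x + 1) and the 97.5% quantile of Beta(x + 1, n − x). For 5/20 these are 0.08657 and 0.49105, as tabulated; all 19 rows reproduce to rounding (largest difference 0.000005). The input is a count and the output is a proportion. DoR under SAP 7.6 is a number of weeks, censored for subjects still in response. There is no x out of n, and 0.087 to 0.491 is not an interval for a duration. SAP 3.1 and SAP 7.7 therefore cannot both be followed for DoR.

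**2. The scan calendar.** The Protocol 3.2 flowchart schedules on-treatment disease assessments on days 57, 113, 169, 225 and 281 (Weeks 9, 17, 25, 33, 41). SAP 2.2 sets Week 8 at Cycle 3 Day 1 (day 57) and Week 24 at Cycle 7 Day 1 (day 169).

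**3. Reading A: responded by the landmark.** Responses first seen on days 225 and 281 fall outside the Week 24 set. That is 2 of the 5 scheduled on-treatment scans, plus any response first seen on the 8-weekly follow-up scans. This counts scan slots, not subjects. The documents give no late-response rate. If 0%, 10% or 20% of an assumed 5 responders were that late, the number left out would be 5 × (0, 0.1, 0.2) = 0, 0.5 or 1.

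**4. Reading B: in response at the landmark.** A subject first responding on day 57 is in the Week 24 set only if the response lasts beyond (169 − 57)/7 = 16 weeks. One first responding on day 113 needs more than (169 − 113)/7 = 8 weeks. Assume exponential DoR with true median m:

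- Share of Week 9 responders kept: 0.5^(16/m).
- Their median, by the memoryless property: 16 + m.
- Confirmation already selects somewhat. If it comes from the next scheduled scan 8 weeks later, the median in all confirmed responders is 8 + m.
- With an assumed mix of first responses (60/20/10/10% at Weeks 9/17/25/33) and the same 8-week confirmation, Week 17 and Week 25 responders in the subset need more than 8 weeks. The Week 24 subset median x solves 0.9 × 0.5^(x/m) = 0.5 × [0.6 × 0.5^(16/m) + 0.3 × 0.5^(8/m)]. For m = 24 the bracket is 0.378 + 0.238 = 0.616, so x = 24 × log2(1.8/0.616) = 37.1.

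| m (weeks) | Week 9 responders kept | Their median (16 + m) | All confirmed (8 + m) | Week 24 subset, mixed onset |
|---|---|---|---|---|
| 12 | 40% | 28 | 20 | 24.9 |
| 24 | 63% | 40 | 32 | 37.1 |
| 36 | 74% | 52 | 44 | 49.2 |
| 52 | 81% | 68 | 60 | 65.2 |

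For Week 9 responders, Reading B raises the median by 16 weeks over the unselected value and by 8 weeks over all confirmed responders, since (16 + m) − (8 + m) = 8. With mixed onset, the excess over all confirmed responders is about 5 weeks (24.9 − 20 = 4.9, up to 65.2 − 60 = 5.2). The Week 8 set is not length-selected in this way, because day 57 is the first scheduled on-treatment scan, but it leaves out every response first seen at the other four scans.

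**5. Confirmation.** A day-57 response can be confirmed from day 57 + 28 = 85 (next scheduled scan day 113), and a day-169 response from day 197 (next scan day 225). If confirmation had to fall by the landmark, the Week 8 set would be empty on scheduled scans. SAP 7.2 sets a minimum gap and no deadline, so this is not its natural reading.

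**The case against.** **SAP 3.1 is only a general convention.** SAP 7.6 and 7.7 are the specific sections, and a programmer would almost certainly use Kaplan-Meier. That limits the practical effect. The sentence is still wrong, and the SAP states no order of precedence.

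**The 8- and 24-week medians may be extra displays beside an overall DoR.** SAP 7.4 reports PFS at both landmarks and overall, and the SAP change history says Section 7 was aligned with mock shells that are not in the documents. If so, nothing is excluded. This stands as a possible reading, so it cannot be said that late responses are definitely left out. But SAP 7.4 names an overall result and SAP 7.6 does not.

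**Protocol 4.2.1.3 defines an interval, not a reporting population.** True. The departure is that a restriction appears in one bullet and nowhere else.

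Three stronger inferences are tempting and not supported:

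- *That SAP 7.6 contradicts the Kaplan-Meier method.* A Kaplan-Meier median can be computed in any subset; the disagreement is over the analysis set.
- *That two interval methods would give different medians.* An interval method does not change the point estimate. Only the choice of set does.
- *That SAP 7.2 biases the 8- or 24-week ORR by recoding unconfirmed responses.* With no deadline, later confirmation is already allowed. Protocol 4.2.1 places the efficacy analysis when the last subject completes On Study Follow-up or 12 cycles. Interim analyses are optional, with no stated timing or size, so the documents support no figure for a shortfall.

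**Conclusion.** The point holds, as a minor one. The binomial interval for DoR in SAP 3.1 is an error: it is invalid for a censored time, is inconsistent with SAP 7.7 and is not on the protocol's list. The landmark phrase in SAP 7.6 leaves the DoR analysis set unclear, and both main readings depart from the unrestricted definition, one by dropping late first responses and the other by favoring long ones. The 5- to 16-week inflation applies only to the in-response reading of the Week 24 set. It rests on assumed exponential durations, assumed medians of 12 to 52 weeks and, for the lower end, an assumed onset mix and 8-week confirmation. No DoR value for this trial can be derived from the documents. Confirmation timing in SAP 7.2 needs clarification only. The primary safety objective is untouched.

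**What to change.** - **SAP 3.1:** remove DoR from the binomial-interval sentence, leaving ORR and DCR.
- **SAP 7.6, last bullet:** delete the reference to 8 and 24 weeks. State that the Kaplan-Meier median DoR, with its Kaplan-Meier-based 95% interval, is reported by arm for all confirmed responders, as in SAP 7.7.
- **SAP 7.2 (optional, one line):** a CR or PR at the Week 9 or Week 25 assessment may be confirmed by a later scan at least 4 weeks after the criteria were first met. At any interim, responses awaiting that scan are labelled unconfirmed rather than stable disease.

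The cost is SAP wording and matching table shells. No scans, visits or data are added.

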### 7.7 Analysis of Time to Event (TTE) Variables

Progression Free Survival (PFS), OS and DoR will be analyzed using the Kaplan-Meier product limit estimates along with the corresponding number of subjects at risk. The Duration of follow-up (in months) will be analyzed using the Reverse Kaplan-Meier product limit estimation method.

For all time to event analyses the number of events, number censored, 25th percentile, median, 75th percentile, corresponding 95% CIs as well as the minimum and maximum survival time will be presented in tables. In addition, survival curves will be presented graphically.

## 8.0 TRIAL DRUG EXPOSURE AND COMPLIANCE

Extent of treatment exposure to durvalumab, will be assessed for each of the two study arms. Durvalumab exposure (Arms A and B) will be summarized by the following parameters:

- Duration of durvalumab treatment (week), calculated as:  $(\text{Last dose date} - \text{first dose date} + 1) / 7$
- Number of durvalumab doses
- Total durvalumab dose (mg), defined as the sum of the actual doses (mg) administered
- Number of subjects with durvalumab dose de-escalated (only in Arm A)

Tremelimumab exposure (Arm B) will be summarized by the following parameters:

- Duration of Tremelimumab treatment (week), calculated as:  $(\text{Last dose date} - \text{first dose date} + 1) / 7$
- Number of tremelimumab doses
- Total Tremelimumab dose (mg), defined as the sum of the actual doses (mg) administered

BI 1361849 exposure (Arms A and B) will be summarized by the following parameters:

- Duration of BI 1361849 treatment (week), calculated as:  $(\text{Last dose date} - \text{first dose date} + 1) / 7$
- Number of doses
- Total BI 1361849 dose ( $\mu\text{g}$ ), defined as the sum of the actual doses (mg) administered

## 9.0 SAFETY ANALYSIS

### 9.1 Adverse Events

Adverse events (AEs) will be coded using MedDRA v20 or later and will be classified by System Organ Class (SOC) and preferred term (PT).

Severity of AEs will be assessed according to CTCAE (v4.03).

Prior AEs are those occurring after subject sign off the informed consent and before the administration of the first dose of study treatment.

Drug-relatedness to the study drugs is captured in five categories as follows:

- Definitely related (The AE is clearly related to the investigational agent)

- Probably related (The AE is likely related to the investigational agent)
- Possibly related (The AE may be related to the investigational agent)
- Unlikely related (The AE is doubtfully related to the investigational agent)
- Unrelated (The AE is clearly not related to the investigational agent)

TEAEs are considered as related to the study drug if entered as definitely, probably or possibly related to study drug as assessed by the Investigator. If a subject has multiple occurrences of the same system organ class (SOC) or preferred term, then only the most severe event will be summarized in the tables for that SOC and preferred term.

### 9.1.1 Treatment-Emergent Adverse Events

Treatment-emergent adverse events (TEAEs) are defined as any AEs that started after dosing or worsened in severity after dosing.

An overall AE summary for number of subjects will be presented for the following categories:

- Any Adverse Event
- Any TEAE
- Any Deaths within the AE reporting period
- Any study drug-related adverse event (TRAE) (i.e., related to durvalumab, tremelimumab and/or vaccine)
  - Any durvalumab related TRAE
  - Any tremelimumab related TRAE
  - Any vaccine related TRAE
- Any TEAE  $\geq$  CTCAE Grade 3
- Any TRAE  $\geq$  CTCAE Grade 3
- Any treatment-emergent Serious AEs (SAEs)
- Any Serious TRAEs
- Any TEAE leading to treatment (durvalumab, tremelimumab, and/or vaccine) discontinuation
  - Related to durvalumab
  - Related to tremelimumab
  - Related to vaccine

The following events will be tabulated by SOC and PT. Summaries will be sorted by decreasing frequency of PT within SOC which is sorted alphabetically.

- TEAEs by SOC and PT
- TEAEs by PT frequency only
- Treatment-emergent SAEs
- Treatment-related AEs
  - Durvalumab related
  - Tremelimumab related
  - Vaccine related
- Treatment-related SAEs
- TEAEs leading to treatment (durvalumab, tremelimumab, and/ or vaccine) discontinuation
  - Durvalumab discontinuation
  - Tremelimumab discontinuation
  - Vaccine discontinuation
- DLTs

A summary of TEAEs by SOC, PT and maximum severity, sorted by decreasing frequency of PT within SOC which is sorted alphabetically, will also be provided for:

- TEAEs
- TEAEs  $\geq$  CTCAE Grade 3
- Treatment related AEs
  - Durvalumab related
  - Tremelimumab related
  - Vaccine related
- TRAEs  $\geq$  CTCAE Grade 3

In tabulation by severity grade,

- For a given SOC, only the most severe SOC for each subject will be included.
- For a given PT, only the most severe PT for each subject will be included.

The following listings will be provided:

- All AEs (flag TEAE)

- DLTs
- SAEs
- TEAEs leading to study treatment discontinuation
- TEAEs leading to study drug (durvalumab or tremelimumab) dose modifications
- Deaths in the AE reporting period

#### **9.1.2 Adverse Events of Special Interest (AESIs)**

AESIs will not be separately presented in this analysis.

#### **9.2 Clinical Laboratory Data**

Clinical Laboratory data (chemistry, hematology, coagulation, and urinalysis) will be collected as specified in the study flowchart in section 3.2 of the protocol.

The Clinical lab tests are summarized in Table 3 below.

**Table 3. Clinical Laboratory Tests**

Clinical Chemistry	Hematology	Coagulation	Urinalysis
Alanine transaminase (ALT)	Hematocrit	Activated partial thromboplastin time (aPTT)	Albumin
Albumin	Hemoglobin	Prothrombin time (PT)	Bilirubin
Alkaline phosphatase	Mean cellular volume (MCV)	INR	Blood/Hemoglobin
Aspartate aminotransferase (AST)	Mean corpuscular hemoglobin (MCH)		Glucose
Blood Urea Nitrogen (BUN)	Mean corpuscular hemoglobin concentration (MCHC)		Ketones
Calcium	Mean Platelet Volume (MPV)		White Blood Cells
Carbon Dioxide (CO 2 )	Platelet count		Nitrite
Chloride	Red blood cell (RBC) count		pH
Creatinine	RBC Distribution Width (RDW)		Protein
Glucose	White blood cell (WBC) count		Red Blood Cells
Lactate Dehydrogenase (LDH)	Differential (% and absolute count for each) including:		Specific gravity
Magnesium	Basophils		Urobilinogen
Potassium	Eosinophils		Color
Sodium	Lymphocytes		Turbidity
Total bilirubin	Monocytes		
Total Protein	Neutrophils		
Lipase			
Amylase			
Free T3			
Free T4			
TSH			

**The clinical lab data will be presented in tables and listings as follows:**

- All laboratory results will be presented in the listings.

- Abnormal laboratory values with their clinical significance status will be presented in a listing.
- Urinalysis data, differentials (%), and RDW will be presented in listings only
- Magnesium, MCV, MCH, MCHC, MPV, differentials (absolute count), aPTT, PT, and INR will be presented in listings and summary tables but NOT in shift tables.
- The remaining analytes will be presented in listings, summary tables and shift tables

**The following summaries will be presented:**

- Overall values by time point utilizing continuous descriptive statistics for each arm and cohort.
- For categorical parameters, the n and percentage will be displayed for each arm and cohort.
- Frequencies and percentages for the shifts in these categories (i.e., low to normal, low to high, high to low, etc.) from baseline to each post-treatment assessment time point. For each continuous laboratory parameter, results will be categorized as low, normal, or high based on the laboratory normal ranges. Frequencies and percentages will be presented by Arm A and Arm B and overall Safety population for the shifts in these categories from baseline to selected post-treatment assessment time points (e.g., low to normal, low to high, high to low). Percentages for the shift tables will be calculated based on the number of subjects who had results for both baseline and the corresponding post-treatment assessment time point.
- For continuous parameters, descriptive statistics will be presented for the changes from baseline to each selected post-treatment assessment time point.

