#### 4.1.1 Endpoints and Assessment Methods

Clinical laboratory tests, vital signs and weight measurements, physical exams, ECG, ECOG performance status evaluation, imaging scans and any other medically indicated assessments, including subject interviews, will be performed (as detailed in Section 3.2) to detect new abnormalities and deteriorations of any pre-existing conditions. The investigator will evaluate any laboratory abnormalities for clinical significance, and clinically significant abnormalities will be recorded as adverse events. All treatment-emergent clinically significant abnormalities and deteriorations from time of signing the informed consent to the end of study visit will be recorded in the Case Report Forms as adverse events and graded according to the CTCAE Version 4.03. See further adverse event documentation and reporting requirements in Section 7.1.

For the dose evaluation phase, DLTs and RCDs will be assessed as per Sections 3.1.9 and 3.1.7.1, respectively.

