#### 4.1.2 Subject Evaluation and Statistics

The **Per-Protocol (PP) Population for DLT Assessment** includes:

- All subjects who experience a DLT at any time during the DLT Evaluation Period (as defined in Section 3.1.9)
- All subjects with no DLT who receive at least 75% of the scheduled doses of durvalumab and tremelimumab and at least 4 of the 5 BI 1361849 vaccinations as well as respective safety assessments without major protocol violations during the DLT Evaluation Period (as defined in Section 3.1.9)

Refer to Section 3.1.11 for subject replacement.

CONFIDENTIAL

The **Safety Population** is defined as all subjects who receive at least one dose of any of the study drugs.

In the dose evaluation phase, for the primary endpoint of determining DLTs and the RCD, the analysis of safety and tolerability will be based on the **PP Population for DLT Assessment**.

In both phases (evaluation and expansion), the overall analysis of safety and tolerability will be based on the **Safety Population**.

Appropriate summaries of AEs, SAEs, laboratory data and vital signs data will be presented for the Safety Population overall and by cohort. Adverse events will be coded using the MedDRA dictionary. Incidences of treatment-emergent adverse events (TEAE, those events that started after dosing or worsened in severity after dosing) will be presented overall and by maximum severity and relationship to study drugs.

For each continuous laboratory parameter, results will be categorized as low, normal, or high based on the laboratory normal ranges. Frequencies and percentages will be presented for the shifts in these categories (i.e., low to normal, low to high, high to low, etc.) from baseline to each post-treatment assessment time point. Additionally, for each continuous hematology and chemistry parameter, descriptive statistics will be presented for the changes from baseline to each post-treatment assessment time point. Descriptive statistics will be presented for the changes in vital signs from baseline to each post-treatment assessment time point.

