## 2.2 Study Endpoints

### Primary Endpoints

The primary endpoint of the combination therapy of durvalumab and tremelimumab are:

- Dose- Limiting Toxicities (DLTs). DLTs are defined as any adverse events that are possibly, probably, or definitely related to the administration of durvalumab, tremelimumab, or BI 1361849 components. This applies to Dose Evaluation subjects during the DLT Evaluation period.
- Safety and tolerability evaluated using CTCAE 4.03.
- Recommended Combination Dose (RCD) determined in Dose Evaluation Phase.

The safety endpoints for this study include:

[figure not shown]
- Treatment-emergent adverse events (TEAEs) and serious AEs (SAEs)
- Clinical laboratory tests (hematology and chemistry)
- Vital signs and weight measurements
- ECG
- ECOG performance status evaluation
- Any other medically indicated assessments, including subject interviews
- All safety analyses will be reported separately for Arm A and Arm B

The Clinical efficacy endpoints will be assessed by irRECIST and RECIST 1.1 and will include:

- Objective Response rate (ORR) at 8 and 24 weeks. ORR is defined as the percentage of subjects meeting criteria of Complete Response (CR) or Partial Response (PR) over a period of at least 4 weeks.
- Duration of Response (DoR). DoR is defined as the interval between the date of earliest determination of CR or PR to the date of earliest determination of PD, or to the date of death, if PD does not occur.
- Disease Control rate (DCR). DCR is defined as the percentage of subjects meeting criteria of Stable Disease (SD), PR, or CR over a period of at least 4 weeks.
- Progressive Free Survival (PFS) at 8 and 24 weeks. PFS is defined as the interval between the date of first dose to the date of earliest determination of Progressive Disease

(PD), or to the date of death, if PD does not occur. Week 8 corresponds to Cycle 3 Day 1 and Week 24 corresponds to Cycle 7 Day 1.

- Overall Survival (OS). OS is defined as the interval between the date of first dose until the date of death or the date of last follow-up.
- All efficacy analyses will be reported separately for Arm A and Arm B.

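### Laboratory shift tables carry no CTCAE grade and omit neutrophils, lymphocytes and magnesium, so graded laboratory worsening reaches the tables only through investigator judgement

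*SAP*

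**What the plan says.** Protocol 4.1.2 sets the shift rule and allows no exceptions: "For each continuous laboratory parameter, results will be categorized as low, normal, or high based on the laboratory normal ranges". SAP 9.2 repeats it: "results will be categorized as low, normal, or high based on the laboratory normal ranges".

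Earlier in the same section, however, the SAP narrows the set of analytes: "Magnesium, MCV, MCH, MCHC, MPV, differentials (absolute count), aPTT, PT, and INR will be presented in listings and summary tables but NOT in shift tables". It adds: "Urinalysis data, differentials (%), and RDW will be presented in listings only". The remaining analytes get listings, summaries and shifts.

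SAP 2.2 gives as a primary endpoint "Safety and tolerability evaluated using CTCAE 4.03", and lists hematology and chemistry tests separately among the safety endpoints.

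Laboratory values reach a CTCAE grade by one route. Under protocol 4.1.1 the investigator reviews abnormalities, and "clinically significant abnormalities will be recorded as adverse events" and graded by CTCAE 4.03. SAP 9.1.1 tabulates treatment-emergent events by maximum severity and separately at Grade 3 or above. SAP 9.2 lists all results, and lists abnormal values with their clinical significance status but not their grade. Neither document plans a laboratory table by CTCAE grade.

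**The concern.** Low, normal and high say whether a value left the reference range, not how far. Two kinds of information are lost. A subject already outside the range at entry cannot register further worsening in the same direction. A subject normal at entry registers that a limit was crossed, but a slight and a severe excursion fall in the same cell.

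Abnormal entry values are allowed. Protocol 5.1 criterion 5 admits AST, ALT and alkaline phosphatase up to 2.5 times ULN, bilirubin up to 1.5 times ULN, hemoglobin from 9 g/dL and lymphocytes from 400 cells/µL. Amendment 8 lowered the lymphocyte limit from 800 because it was keeping out otherwise qualified subjects. Lymphocytes are then among the analytes with no shift table.

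At stake is whether a reader of the report can count subjects by worst laboratory grade without relying on each investigator's view of clinical significance.

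**Working it through.** The plan gives no figure to reproduce. The check has three parts: classify example values, count the analytes, and compare the texts.

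**1. Classification.** Rule: high if the value exceeds 1 × ULN, otherwise normal. I assume that the ULN used for eligibility and grading is the upper end of the laboratory normal range. Severity markers come from protocol 3.1.9, which puts the top of Grade 2 at 5 × ULN for transaminases and 3 × ULN for bilirubin.

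| Analyte | Baseline (× ULN) | Later (× ULN) | Shift cell | Above the Grade 2 limit? |
|---|---|---|---|---|
| ALT | 2.5 | 2.6 | high to high | no |
| ALT | 2.5 | 5.1 | high to high | yes (5.1 > 5) |
| ALT | 0.8 | 2 | normal to high | no |
| ALT | 0.8 | 9 | normal to high | yes (9 > 5) |
| Bilirubin | 1.5 | 1.6 | high to high | no |
| Bilirubin | 1.5 | 3.1 | high to high | yes (3.1 > 3) |

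Within each pair the shift cell is the same, although one value is within the Grade 2 limit and the other above it. The baselines of 2.5 and 1.5 are the entry limits. The documents give no CTCAE cut-offs for neutrophils, lymphocytes or magnesium, so there is no example for them.

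**2. Analytes without a shift table.** SAP Table 3 has 21 chemistry, 15 hematology (each differential cell type counted once) and 3 coagulation analytes: 21 + 15 + 3 = 39. Excluded are magnesium (1), MCV, MCH, MCHC and MPV (4), five absolute differentials (5) and aPTT, PT and INR (3), which makes 13. RDW, in listings only, brings this to 14. That leaves 39 − 14 = 25 with shift tables.

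**3. The texts side by side.**
- Protocol 4.1.2 plans shifts for each continuous parameter; SAP 9.2 excludes 14.
- SAP 9.2 still says each continuous parameter when it describes the shifts, so it conflicts with its own exclusion list.
- SAP 1.0 says that the SAP sets out differences from the protocol's methods. This one is not identified.
- SAP 9.2 says both each and selected post-treatment time points for the shifts.

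**4. A case the protocol foresees.** One DLT exception in protocol 3.1.9 is a pre-existing laboratory abnormality that deteriorates to Grade 3 or 4, where investigator and sponsor both consider the increment not clinically significant. Under 4.1.1 such a change need not be recorded as an adverse event. It would then enter no graded table, and its shift cell could be high to high or low to low.

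**The case against.** The strongest reply is that the primary endpoint is already served by graded adverse events and DLTs. Protocol 4.1.1 covers deterioration of pre-existing conditions, so an abnormal baseline is no barrier. SAP 9.1.1 counts events that worsened after dosing. Neutrophils, lymphocytes and magnesium stay in the summary tables, change-from-baseline statistics are planned, and every value is listed. The three-category rule is the protocol's own, the analysis is descriptive with about 20 subjects per arm, and neither document promises a graded laboratory table. All of this stands.

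It also rules out several stronger readings that a reader might infer:
- *Worsening from an abnormal baseline is invisible.* It is not, for the reasons above.
- *A very large transaminase rise could go unreported.* This is among the least likely losses. For immune-related hepatitis, protocol 8.3.1 attaches permanent discontinuation to transaminases above 8 × ULN. A related rise above that level also falls outside the liver exemption in 3.1.9. SAP 9.1.1 tabulates discontinuations, DLTs and events of Grade 3 or above.
- *Lymphocytes belong in shift tables because lymphopenia bears on DLTs.* Protocol 3.1.9 exempts Grade 3 and 4 lymphopenia without condition.
- *A number of affected subjects per arm can be given.* The documents report no rates of abnormal baseline values.

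The reply does not close the gap for changes judged not clinically significant. The general adverse event definition in protocol 7.1.1 includes abnormal laboratory findings, but 4.1.1 makes clinical significance the test for recording them. Summary statistics can show an extreme value, but they do not count subjects by grade. The exclusions may be deliberate, but the SAP does not label them as a departure or give a reason.

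**Conclusion.** The point holds in a limited form. The shift tables cannot show severity within the abnormal range, and 14 of 39 analytes, including absolute neutrophils, absolute lymphocytes and magnesium, have no shift table. That exclusion departs from protocol 4.1.2 without being declared and conflicts with the SAP's own wording. As a result there is no graded laboratory tabulation independent of the investigator, and worsening judged not clinically significant can be absent from every graded table.

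The size is small. No test or sample size depends on it, and the raw values remain available in listings. Omitting the coagulation tests matters little, because they are scheduled only at screening and the first On Study Follow-up visit unless clinically indicated. How many subjects are affected cannot be estimated from the documents. This is a cheap improvement and does not undermine the safety analysis.

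**What to change.** In SAP 9.2:
1. Add a table, by arm, of baseline CTCAE 4.03 grade against worst post-baseline grade for every gradable analyte, including absolute neutrophils, absolute lymphocytes and magnesium. SAP 9.4 already uses the worst post-baseline assessment for ECGs.
2. Keep low/normal/high shifts for analytes that have no CTCAE grade.
3. For the other excluded analytes, either restore the shift tables or state that the exclusion departs from protocol 4.1.2 and give the reason.
4. Align the wording on each continuous parameter with the exclusion list, and settle whether shifts are shown at each or at selected time points.

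The cost is modest: grade derivations programmed from data already collected, and some extra table output. No additional visits or samples are needed.
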